### **10.4.2 Analysis of Secondary Endpoints**

Table 2 summarizes the secondary efficacy endpoint(s) and summary of planned analyses for select secondary outcomes. Unless otherwise stated, point estimates in the form of mean differences or odds ratios along with 95% confidence intervals will be reported descriptively for secondary outcomes.

An exploratory assessment using the MCID will be done for select secondary outcomes. The MCID will be used to explore the clinical importance of the mean difference between treatment groups for all patient-reported outcomes (i.e. ASES, SANE, and Constant-Murley score). The MCID used for outcomes related to the ASES score, SANE score and Constant-Murley score will be 11.1 points, 29.4 points, and 5.5 points, respectively. For outcomes involving the ASES-VAS pain score, the MCID used will be 1.37 cm^26.

This document contains information that is confidential and proprietary to Smith & Nephew PLC and Smith & Nephew, Inc. and is intended for use only by Smith & Nephew and its manufacturer. It shall not be reproduced or copied in whole or in part, nor shall the contents be disclosed by any means without prior written permission from Smith & Nephew, nor shall anyone make any use of it that is contrary to the expressed or implied wishes of Smith & Nephew.

Prospective multi-center study comparing REGENETEN in lieu of standard arthroscopic repair of high-grade (>50%) partial-thickness tears

Number: REGEN.PUB.2018.09 Version: 3.0, 10SEP2019 Page: Page 38 of 105

smith&nephew

Item	Objective	Outcome Measure	Statistical Test	
Secondary Objective #1	To determine if there are early benefits (within 3 months of surgery) of arthroscopic surgical treatment of high-grade (>50%) partial-thickness rotator cuff tears using REGENETEN on participant-reported daily shoulder function/disability and pain compared to standard surgical repair techniques.	American Shoulder and Elbow Surgeons (ASES) Score weekly through 3 months post-index surgery.	Generalized linear regression adjusting for baseline ASES score and differences in baseline characteristics. The mean ASES scores will be compared using an MCID of 11.1 points.	
Secondary Objective #2	To determine if there are early benefits (within 3 months of surgery) of arthroscopic surgical treatment of high-grade (>50%) partial-thickness rotator cuff tears using REGENETEN on participant-reported average shoulder function as a percentage of normal compared to standard surgical repair techniques.	Simple Assessment Numeric Evaluation (SANE) Score weekly through 3 months post-index surgery.	Generalized linear regression adjusting for baseline SANE score and differences in baseline characteristics. The mean SANE scores will be compared using an MCID of 29.4 points.	
Secondary Objective #3	To determine if there are early benefits (within 3 months of surgery) of arthroscopic surgical treatment of high-grade (>50%) partial-thickness rotator cuff tears using REGENETEN on participant-reported shoulder pain compared to standard surgical repair techniques.	VAS pain score from the American Shoulder and Elbow Surgeons (ASES) Score weekly through 3 months post-index surgery.	Generalized linear regression adjusting for baseline VAS pain score and differences in baseline characteristics. The mean ASES-VAS pain score will be compared using an MCID of 1.37 cm.	
Secondary Objective #4	To determine if arthroscopic surgical treatment of high-grade (>50%) partial-thickness rotator cuff tears using REGENETEN yields statistically improved participant-reported composite of daily shoulder function/disability and pain compared to standard surgical repair techniques over the	American Shoulder and Elbow Surgeons (ASES) Score at 6, 12, 18 and 24 months.	Generalized linear regression adjusting for baseline ASES score and differences in baseline characteristics. The mean ASES scores will be compared using an MCID of 11.1 points.	

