- 14. Earlier return to driving
- 15. Earlier return to sports
- 16. Lower incidence of progression to full-thickness tear (within 12 months following index surgery)
- 17. Lower incidence of progression to full-thickness tear (within 24 months following index surgery)
- 18. Increased percent filling of rotator cuff (at 12 months following index surgery)
- 19. Increased percent filling of rotator cuff (at 24 months following index surgery)
- 20. Improvements in rotator cuff tendon thickness (at 12 months following surgery)
- 21. Improvements in rotator cuff tendon thickness (at 24 months following surgery)

This document contains information that is confidential and proprietary to Smith & Nephew PLC and Smith & Nephew, Inc. and is intended for use only by Smith & Nephew and its manufacturer. It shall not be reproduced or copied in whole or in part, nor shall the contents be disclosed by any means without prior written permission from Smith & Nephew, nor shall anyone make any use of it that is contrary to the expressed or implied wishes of Smith & Nephew.

Study Protocol—Device	%smith&nephew
Prospective multi-center study comparing REGENETEN in	Number: REGEN.PUB.2018.09
neu of standard arthroscopic repair of high-grade (>50%)	Version: 3.0, 10SEP2019 Page: Page 16 of 105

- 22. Lower fatty infiltration of the rotator cuff (at 12 months following surgery)
- 23. Lower fatty infiltration of the rotator cuff (at 24 months following surgery)
- 24. Improved rotator cuff integrity (at 12 months following surgery)
- 25. Improved rotator cuff integrity (at 24 months following surgery)
- 26. Lower incidence of revision surgery (index shoulder; all causes) (within 24 months following index surgery)
- 27. Lower aggregate health care utilization costs (over 12 months following index surgery)
- 28. Decreased operating room time (index surgery)
- 29. Fewer shoulder steroid injections (over 12 months following index surgery)
- 30. Fewer unscheduled index shoulder-related clinic visits (over 12 months following index surgery)
- 31. Fewer for-cause imaging procedures (over 12 months following index surgery)
- 32. Fewer physiotherapy sessions (over 12 months following index surgery)

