#### 8.2 ALLOCATION AND BLINDING

This study is not randomized. Selection of the surgical approach (repair with REGENETEN versus standard repair techniques) will be at the discretion of the Investigator, in consultation with the participant, as appropriate.

Standard surgical repair techniques of the rotator cuff will be defined as either:

- 1. Debridement and a transtendinous repair, or
- 2. Complete takedown and repair.

To ensure an equal number of participants enrolled into each treatment group, the Sponsor and Contract Research Organization (CRO) will continuously monitor enrollment and will close enrollment into the faster enrolling cohort (REGENETEN cohort or standard repair technique

This document contains information that is confidential and proprietary to Smith & Nephew PLC and Smith & Nephew, Inc. and is intended for use only by Smith & Nephew and its manufacturer. It shall not be reproduced or copied in whole or in part, nor shall the contents be disclosed by any means without prior written permission from Smith & Nephew, nor shall anyone make any use of it that is contrary to the expressed or implied wishes of Smith & Nephew.

Study Protocol—Device	Smith&nephew
	Number:           REGEN.PUB.2018.09           Version: 3.0, 10SEP2019           Page: Page 25 of 105

cohort) once the targeted enrollment has been reached. Enrollment into the slower enrolling cohort will continue until the study is fully enrolled.

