#### 10.1 GENERAL

The CRO's Biostatistician will conduct the statistical analyses for this study, with the exception of the economic analysis, which will be conducted by Smith & Nephew's Global Biostatistics group. For the primary outcome, the significance tests and hypothesis testing will be two-sided, performed at the 5% significance level. Resulting p-values will be quoted and 95% two-sided confidence intervals will be generated where appropriate. Unless otherwise stated, point estimates (mean differences or odds ratios) and 95% confidence intervals will be reported descriptively for secondary outcome as an exploratory assessment. Select secondary outcomes will undergo statistical testing as outlined in section 10.4.2.

Where data summaries are specified, categorical and ordinal variables will be summarized with frequencies and percentages. Continuous variables will be summarized with the following summary statistics: number of observations, means and standard deviations, or median and interquartile ranges. All analyses will be performed using a statistical package such as SAS or SPSS.

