#### CONFIDENTIAL AND PROPRIETARY

## Prospective multi-center study comparing REGENETEN in lieu of standard arthroscopic repair of high-grade (>50%) partial-thickness tears

Number: REGEN.PUB.2018.09 Version: 3.0, 10SEP2019 Page: Page 42 of 105

smith&nephew

ltem	Objective Outcome Statistical Measure		Statistical Test
	thickness tears (diagnosed by MRI) compared to participants who had standard surgical repair at 24 months from the index shoulder surgery.		
Secondary Objective #18	To determine if participants who undergo arthroscopic surgical treatment of high-grade (>50%) partial-thickness rotator cuff tears using REGENETEN have increased percent filling of the rotator cuff (based on MRI assessment) compared to participants who had standard surgical repair at 12 months from the index shoulder surgery.	Percent filling (based on MRI assessment) at 12-months post- surgery	N/A
Secondary Objective #19	To determine if participants who undergo arthroscopic surgical treatment of high-grade (>50%) partial-thickness rotator cuff tears using REGENETEN have increased percent filling of the rotator cuff (based on MRI assessment) compared to participants who had standard surgical repair at 24 months from the index shoulder surgery.	Percent filling (based on MRI assessment) at 24-months post- surgery.	N/A
Secondary Objective #20	To determine if participants who undergo arthroscopic surgical treatment of high-grade (>50%) partial-thickness rotator cuff tears using REGENETEN have improvements in rotator cuff tendon thickness (based on MRI assessment) compared to participants who had standard surgical repair at 12 months from the index shoulder surgery.	Rotator cuff tendon thickness (based on MRI assessment) at 12-months post- surgery.	Generalized linear regression adjusting for baseline tendon thickness and differences in baseline characteristics
Secondary Objective #21	To determine if participants who undergo arthroscopic surgical treatment of high-grade (>50%)	Rotator cuff tendon thickness (based on MRI	Generalized linear regression

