#### CONFIDENTIAL AND PROPRIETARY

## Prospective multi-center study comparing REGENETEN in lieu of standard arthroscopic repair of high-grade (>50%) partial-thickness tears

Number: REGEN.PUB.2018.09 Version: 3.0, 10SEP2019 Page: Page 43 of 105

smith&nephew

Item	Objective	Outcome Measure	Statistical Test
	partial-thickness rotator cuff tears using REGENETEN have improvements in rotator cuff tendon thickness (based on MRI assessment) compared to participants who had standard surgical repair at 24 months from the index shoulder surgery.	assessment) at 24-months post- surgery.	adjusting for baseline tendon thickness and differences in baseline characteristics.
Secondary Objective #22	To determine if participants who undergo arthroscopic surgical treatment of high-grade (>50%) partial-thickness rotator cuff tears using REGENETEN have a statistically lower fatty infiltration of the rotator cuff (based on MRI assessment) compared to participants who had standard surgical repair at 12 months from the index surgery.	Goutallier classification of rotator cuff (based on MRI assessment) at 12-months post- surgery.	N/A
Secondary Objective #23	To determine if participants who undergo arthroscopic surgical treatment of high-grade (>50%) partial-thickness rotator cuff tears using REGENETEN have a statistically lower fatty infiltration of the rotator cuff (based on MRI assessment) compared to participants who had standard surgical repair at 24 months from the index surgery.	Goutallier classification of rotator cuff (based on MRI assessment) at 24-months post- surgery.	N/A
Secondary Objective #24	To determine if participants who undergo arthroscopic surgical treatment of high-grade (>50%) partial-thickness rotator cuff tears using REGENETEN have statistically improved rotator cuff integrity (based on MRI assessment) compared to participants who had standard surgical repair techniques at 12 months from the index surgery.	Sugaya score (based on MRI assessment) at 12-months post- surgery.	N/A

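### Fifteen of the 32 comparative secondary objectives name no model and no covariates, in a non-randomised study that adjusts the primary endpoint and the other 17

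*Combined protocol and SAP*

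**What the plan says.** Section 8.2 sets the allocation: "This study is not randomized. Selection of the surgical approach (repair with REGENETEN versus standard repair techniques) will be at the discretion of the Investigator". Section 10.4.1 adjusts the primary ASES comparison for baseline ASES and for baseline differences between the cohorts.

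For secondary outcomes, section 10.1 says "Select secondary outcomes will undergo statistical testing as outlined in section 10.4.2". Section 10.4.2 then gives the default for any row without its own rule: "point estimates in the form of mean differences or odds ratios along with 95% confidence intervals will be reported descriptively for secondary outcomes". Neither section attaches covariates to that default. Adjustment appears only in the Statistical Test column of Table 2, row by row. The tendon-thickness rows (#20-21), for instance, specify regression "adjusting for baseline tendon thickness and differences in baseline characteristics".

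In 15 rows that column reads N/A. In Table 2, the two Goutallier objectives among them (#22-23) ask whether the REGENETEN cohort has "statistically lower fatty infiltration of the rotator cuff", and the two Sugaya objectives (#24-25) use the same adverb for improved cuff integrity. Section 9.2.1 defines both scales as ordinal: grades 0 to 4 and Types I to V.

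**The concern.** When the surgeon chooses the operation, the cohorts may differ in tear and patient features that also affect healing, costs and use of care. The plan accepts this for the primary endpoint and for 17 secondary rows. For the remaining 15 it prescribes a between-cohort estimate with an interval and nothing to deal with those differences.

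These rows are not peripheral. Section 5.2 frames every secondary objective as a determination of whether REGENETEN does better than standard repair. The objective stated in section 4.1 includes lower health care utilisation, yet the cost row and all four utilisation counts (#27, #29-32) are N/A. Under section 10.6 the one-year analysis may be published, and 11 of the 15 rows (all but the 24-month rows #17, 19, 23 and 25) concern outcomes that fall within that first year or are collected in the 12-month diary. An unadjusted difference with a 95% interval, placed beside adjusted ones, is easily read as a treatment effect of the same standing.

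**Working it through.** The plan gives no figure of its own on this point, so the check is a count of Table 2, a comparison of like with like, and an illustration of scale.

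**1. Count of the Statistical Test column**

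- Regression adjusted for baseline differences: #1-11, 13, 15, 20, 21, 26, 28 = 17 rows.
- N/A: #12, 14, 16, 17, 18, 19, 22, 23, 24, 25, 27, 29, 30, 31, 32 = 15 rows.
- 17 + 15 = 32, and 15/32 = 46.9%. Of the 15, ten are performance objectives and five are economic.
- N/A rows worded as statistical superiority: #22, 23, 24, 25 = 4.

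**2. Is there a principle behind the split?**

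| Type of outcome | Adjusted | N/A |
|---|---|---|
| Return to activity, from the diary | work (#13), sports (#15) | driving (#14) |
| MRI, independent reader | tendon thickness (#20-21) | full-thickness tear (#16-17), percent filling (#18-19), Goutallier (#22-23), Sugaya (#24-25) |
| Binary event | revision surgery (#26) | full-thickness tear (#16-17) |
| Economic | operating room time (#28) | costs (#27), counts (#29-32) |

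Neither data source, outcome type nor economic status separates the columns, and the text gives no other reason.

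**3. Are the N/A rows unadjusted?** The documents do not say so. They name no covariates for these rows, whereas every one of the other 17 rows states its adjustment. As context only, the version 3.0 amendment log records that a baseline-adjusted method was removed from eight of these rows (#12, 14, 16, 17, 27, 30, 31, 32). Followed as written, the plan yields crude estimates here.

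**4. Scale of possible bias (assumed inputs, no true treatment effect)**

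The documents give neither imbalance nor prognostic strength, so everything here is illustrative.

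*Binary outcome.* Assume a 10% risk without the risk factor, and a factor with outcome odds ratio 2 present in 30% of the REGENETEN cohort and 50% of the comparison cohort.

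- Risk with the factor: odds 2 × 0.1/0.9 = 0.2222, so risk 0.2222/1.2222 = 0.1818.
- REGENETEN: 0.3 × 0.1818 + 0.7 × 0.1 = 0.1245. Comparison: 0.5 × 0.1818 + 0.5 × 0.1 = 0.1409.
- Crude odds ratio: (0.1245/0.8755)/(0.1409/0.8591) = 0.87.

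With imbalances of 10 to 30 points and factor odds ratios of 1.5 to 3, the crude odds ratio runs from 0.96 to 0.72. Reversing the imbalance gives the reciprocals, 1/0.96 = 1.04 to 1/0.72 = 1.39.

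*Continuous outcome.* Section 11 plans 118 participants with 15% dropout: 118 × 0.85 = 100.3, about 50 per arm. The standard error of a difference is √(2/50) = 0.2 SD. With residual bias b (in SD), the chance that the 95% interval excludes zero is 1 − Φ(1.96 − b/0.2) + Φ(−1.96 − b/0.2):

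- b = 0.1: 7.9%
- b = 0.2: 17.0%
- b = 0.3: 32.3%

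The nominal figure is 5%.

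**The case against.** The strongest reply is that the plan calls these outcomes exploratory and descriptive, tests only selected ones, and describes section 10 as a brief outline with a SAP to follow before database lock. N/A under a column headed Statistical Test may mean only that no test is planned. That limits what may be claimed from these rows, but a label does not remove confounding from a between-cohort estimate and its interval, and the plan as it stands tells the SAP author nothing about adjusting these rows.

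Several stronger readings are tempting and do not hold:

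- *The plan declares these analyses unadjusted, or the estimates are known to be biased.* Neither is stated. The lack of adjustment is an inference, though a strong one; the size and direction of any bias are unknown.
- *A mean difference is assigned to Goutallier and Sugaya grades.* It is not. Section 10.1 summarises ordinal variables by frequencies and percentages, and the default offers mean differences or odds ratios. The gap is that no effect measure is specified.
- *Objectives #22-25 claim significance throughout the protocol.* Section 5.2 states the same objectives without the adverb, so this is a wording mismatch inside Table 2.
- *Publication of these contrasts is planned.* Section 10.6 calls it possible and ties it to the one-year analysis, outside which the four 24-month rows fall.
- *Adjustment would repair all 15 rows.* Sling days (#12) and physiotherapy sessions (#32) largely reflect the cohort-specific guidelines of section 9.1.6, which baseline covariates cannot undo.

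It also stands that the primary analysis names no fixed covariate list, so there is no ready-made set to carry over.

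**Conclusion.** The point holds. For 15 of 32 comparative secondary objectives (47%) the plan gives only a default estimate with no covariates, in a study where treatment is chosen, and it handles closely similar outcomes in two ways without a reason. These estimates are exposed to confounding that the plan addresses elsewhere. How much, and in which direction, cannot be said from the documents; the figures above rest wholly on assumed imbalances. Four of the rows also carry superiority wording that no planned test supports, and no effect measure is chosen for their ordinal grades. The primary endpoint is unaffected. The change is worth making because it concerns nearly half the secondary objectives and can be made before database lock.

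**What to change.** In section 10.4.2 and the SAP:

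- List one prespecified set of baseline characteristics and report the between-cohort estimates for these rows adjusted for it, by a regression suited to the outcome type or by propensity weights. Proportional odds for #22-25 and a count model for #29-32 are examples. Keep the results exploratory, with no confirmatory claim.
- For #14, also state how participants who do not return to driving are handled.
- Where events are too sparse to adjust, or where the contrast is driven by the cohort-specific care pathway (#12, #32), label the estimate as unadjusted and not supporting a comparative conclusion.
- Delete the word *statistically* from #22-25 in Table 2, to match section 5.2.

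The cost is SAP text and some programming, with no new data collection. Intervals will be wider for sparse outcomes. Baseline MRI covariates may be missing for some participants, because section 9.1.2 obtains the pre-operative scan only if available and section 9.1.8 does not require it to follow the study acquisition protocol. The SAP should say what is done in that case.

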#### **Table 2: Analysis of Secondary Endpoints**

This document contains information that is confidential and proprietary to Smith & Nephew PLC and Smith & Nephew, Inc. and is intended for use only by Smith & Nephew and its manufacturer. It shall not be reproduced or copied in whole or in part, nor shall the contents be disclosed by any means without prior written permission from Smith & Nephew, nor shall anyone make any use of it that is contrary to the expressed or implied wishes of Smith & Nephew.

## Prospective multi-center study comparing REGENETEN in lieu of standard arthroscopic repair of high-grade (>50%) partial-thickness tears

 Number:

 REGEN.PUB.2018.09

 Version: 3.0, 10SEP2019

 Page: Page 39 of 105

smith&nephew

ltem	Objective	Outcome Measure	Statistical Test
	24 months from the index shoulder surgery.		
Secondary Objective #5	To determine if arthroscopic surgical treatment of high-grade (>50%) partial-thickness rotator cuff tears using REGENETEN yields statistically improved participant-reported average shoulder function as a percentage of normal compared to standard surgical repair techniques over the 24 months from index shoulder surgery.	of high-grade ness rotatorAssessment Numeric Evaluation (SANE)regression adjusting for baselin SANE score and differences in basel characteristics. The mean SANE scores will be compared using an MCID of 25	
Secondary Objective #6	To determine if arthroscopic surgical treatment of high-grade (>50%) partial-thickness rotator cuff tears using REGENETEN statistically decreases participant- reported shoulder pain compared to standard surgical repair techniques over the 24 months from the index shoulder surgery.	VAS Pain score from the American Shoulder and Elbow Surgeons (ASES) Score at 6, 12, 18 and 24 months.	Generalized linear regression adjusting for baseline VAS pain score and differences in baseline characteristics. The mean ASES-VAS pain score will be compared using an MCID of 1.37 cm.
Secondary Objective #7	To determine if arthroscopic surgical treatment of high-grade (>50%) partial-thickness rotator cuff tears using REGENETEN statistically improved participant- reported and examiner-assessed shoulder pain and function compared to standard surgical repair techniques over 24 months from the index shoulder surgery.	Constant-Murley Score at 3, 6, 12 and 24 months.	Generalized linear regression adjusting for baseline Constant- Murley score and differences in baseline characteristics. The mean Constant- Murley score will be compared using an MCID of 5.5 points.
Secondary Objective #8	To determine if participants who undergo arthroscopic surgical treatment of high-grade (>50%) partial-thickness rotator cuff tears using REGENETEN use significantly less opioids to treat the index shoulder compared to standard surgical repair over the	Dose/duration of opioid use from post-surgery to 3- months post- surgery. Defined daily dose (DDD) will be used as the outcome measure.	Generalized linear regression adjusting for baseline opioid use and differences in baseline characteristics.

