#### LIST OF ABBREVIATIONS

Abbreviation	Definition
AAROM	Active Assisted Range of Motion
ADE	Adverse Device Effect(s)
ADL	Activities of Daily Living
AE	Adverse Event(s)
AROM	Active Range of Motion
ASADE	Anticipated Serious Adverse Device Effect
ASES	American Shoulder and Elbow Surgeons
CRF	Case Report Form(s)
CRO	Contract Research Organization
CSR	Clinical Study Report
СТА	Clinical Trial Agreement
CV	Curriculum Vitae
DD	Device Deficiency(ies)
DDD	Defined Daily Dosage
EDC	Electronic Data Capture
GCP	Good Clinical Practice
ICF	Informed Consent Form
ICH	International Conference on Harmonisation
ICJME	International Committee of Medical Journal Editors
IFU	Instructions for Use
IP	Investigational Product
IRB	Institutional Review Board
ISF	Investigator Site File
MCID	Minimal Clinically Important Difference

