*Constant-Murley Score:* The Constant-Murley Score is a validated assessment of pain and shoulder functionality. The test is divided into four subscales: pain, activities of daily living, strength and range of motion (forward elevation, external rotation, abduction and internal rotation of the shoulder. At the end of the assessment, a score is obtained out of 100 points where higher scores indicate a higher quality of shoulder function. The score is obtained through a combination of participant-reported and objective (examiner-assessed) shoulder outcome measures.

*Duration of Shoulder Immobilization:* The duration of medically required shoulder immobilization following index surgery will be calculated based on the number of days in a sling, as reported in the participant diary.

*Cumulative opioid use:* Cumulative opioid use to treat the index shoulder from index surgery to 12 months will be calculated based on usage reported in the participant diary (name, dose, duration).

*Cumulative Non-opioid Prescription Medication Use:* Cumulative non-opioid prescription medication use to treat the index shoulder from index surgery to 12 months will be calculated based on usage reported in the participant diary (name, dose, duration).

*Time to Return to Work, Driving, and Sports:* Time from index surgery to return to ADLs will be calculated based on the date that participants report return to work (sedentary; laborer), return to driving, and return to sport as reported in the participant diary.

This document contains information that is confidential and proprietary to Smith & Nephew PLC and Smith & Nephew, Inc. and is intended for use only by Smith & Nephew and its manufacturer. It shall not be reproduced or copied in whole or in part, nor shall the contents be disclosed by any means without prior written permission from Smith & Nephew, nor shall anyone make any use of it that is contrary to the expressed or implied wishes of Smith & Nephew.

Study Protocol—Device	* smith&nephew
	Number:           REGEN.PUB.2018.09           Version: 3.0, 10SEP2019           Page: Page 33 of 105

*Incidence of Progression to Full Thickness Tear*. An independent reviewer will assess MRIs for evidence of progression to a full-thickness tear within 12 months and 24 months of the index surgery. All MRI assessments are detailed in the Image Review Charter.

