#### CONFIDENTIAL AND PROPRIETARY

## Prospective multi-center study comparing REGENETEN in lieu of standard arthroscopic repair of high-grade (>50%) partial-thickness tears

 Number:

 REGEN.PUB.2018.09

 Version: 3.0, 10SEP2019

 Page: Page 40 of 105

smith&nephew

Item	Objective	Outcome Measure	Statistical Test	
	initial 3 months following index surgery.			
Secondary Objective #9	
 
undergo arthroscopic surgical treatment of high-grade (>50%) partial-thickness rotator cuff tears using REGENETEN use significantly less non-opioid prescription medication to treat the index shoulder compared to standard surgical repair over the initial 3 months following index surgery.
 
non-opioid prescription pain medication use from post-surgery to 3-months post- surgery. DDD will be used as the outcome measure.
 
		Generalized linear regression adjusting for baseline non- opioid prescription pain medication use and differences in baseline characteristics.	
Secondary Objective #10	To determine if participants who undergo arthroscopic surgical treatment of high-grade (>50%) partial-thickness rotator cuff tears using REGENETEN use significantly less opioids to treat the index shoulder compared to standard surgical repair over the 12 months from the index shoulder surgery.	Dose/duration of opioid use from post-surgery to 12- months post- surgery. DDD will be used as the outcome measure.	Generalized linear regression adjusting for baseline opioid use and differences in baseline characteristics.	
Secondary Objective #11	To determine if participants who undergo arthroscopic surgical treatment of high-grade (>50%) partial-thickness rotator cuff tears using REGENETEN use significantly less non-opioid prescription medication to treat the index shoulder compared to standard surgical repair over the 12 months from the index shoulder surgery.	Dose/duration of non-opioid prescription pain medication use from post-surgery to 12-months post- surgery. DDD will be used as the outcome measure.	Generalized linear regression adjusting for baseline non- opioid prescription pain medication use and differences in baseline characteristics.	
Secondary Objective #12	To determine if participants who undergo arthroscopic surgical treatment of high-grade (>50%) partial-thickness rotator cuff tears using REGENETEN have a shorter shoulder immobilization	Number of days in a sling	N/A	

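### Opioid use (secondary objectives #8 and #10) is totalled in defined daily doses, which are not weighted for opioid strength, so a drug mix that differs between cohorts could create, hide or reverse a difference

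*Combined protocol and SAP*

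**What the plan says.** Objective #8 in Table 2 (Section 10.4.2) asks whether REGENETEN participants "use significantly less opioids to treat the index shoulder compared to standard surgical repair over the" initial 3 months; objective #10 asks the same over 12 months. For #8 the unit is given as "Defined daily dose (DDD) will be used as the outcome measure", and for #10 the wording is "DDD will be used as the outcome measure". The only other information on the unit is the List of Abbreviations, which expands it as "Defined Daily Dosage". No source or version of the DDD values, potency conversion, rule for combination products or analysis in another unit is given.

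The analysis for both objectives is "Generalized linear regression adjusting for baseline opioid use and differences in baseline characteristics". Section 9.2.1 says: "Cumulative opioid use to treat the index shoulder from index surgery to 12 months will be calculated based on usage reported in the participant diary". The diary items listed there are drug name, dose and duration.

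Section 9.1.7 requires postoperative opioid use to be documented but fixes no drug. Section 8.2 says the study is not randomized and that "Selection of the surgical approach (repair with REGENETEN versus standard repair techniques) will be at the discretion of the Investigator". Section 8.1 describes an unblinded study at up to 12 sites.

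**The concern.** The objective is about the amount of opioid taken. A DDD counts conventional days' worth of each drug. One DDD of a weak opioid and one DDD of a strong opioid each add 1 to the total, so the total mixes how much was taken with which drug was taken.

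That would matter little if every participant had the same opioid, or if randomization balanced the drugs on average. Here neither applies, and the model named in Table 2 contains no term for postoperative drug, surgeon or site. Adding postoperative drug as a covariate would not be a clean remedy either, because it is determined after treatment.

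The error can run against the sponsor as well as for it. If REGENETEN participants had less pain and were given weaker opioids, a DDD total could show no reduction, or even an increase. At stake is the interpretation of two secondary endpoints that have a regression model in Table 2, where many other rows have N/A. Section 10.6 also allows findings from the 3-month extract to be presented.

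**Working it through.** **Plan's own figure.** There is none: the documents state no expected DDD total, drug mix or power for the opioid endpoints. What follows is a check of the mechanism with assumed inputs.

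**Set-up.** Take two opioids, A and B. Let k be the opioid strength in one DDD of B divided by that in one DDD of A, so A is weaker per DDD. Suppose every participant takes the same strength-weighted amount on average, recorded as 1 DDD if on B and k DDDs if on A. If a share s of a cohort is on A,

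mean DDD = (1 − s) + s·k = 1 + s(k − 1).

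With share p in one cohort and q in the other,

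ratio of mean DDDs = [1 + p(k − 1)] / [1 + q(k − 1)].

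**Size of the artefact.** Assume p = 0.40 and q = 0.20. The true ratio is 1 in every row. The last column is 1 − 1/ratio.

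| k | Calculation | Apparent ratio | True reduction in the first cohort that would be exactly hidden |
|---|---|---|---|
| 1 | 1.00/1.00 | 1.00 | 0% |
| 1.5 | 1.20/1.10 | 1.09 | 8.3% |
| 2 | 1.40/1.20 | 1.17 | 14.3% |
| 3 | 1.80/1.40 | 1.29 | 22.2% |

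If the REGENETEN cohort is the one with 40% on A, a true reduction of the size in the last column vanishes and a smaller one changes sign. If the standard-repair cohort is the one with 40% on A, the same percentages appear as a spurious reduction with REGENETEN. If p = q, the ratio is 1 for every k.

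**Sensitivity to the mix.** At k = 2, shares of 60% and 40% give 1.60/1.40 = 1.14; shares of 75% and 25% give 1.75/1.25 = 1.40.

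**Effect on a 5% two-sided test.** Use 51 participants per arm (the pre-dropout figure in Section 11) and a normal approximation. Assume a coefficient of variation CV for strength-weighted consumption. For a cohort with share s on A and mean m,

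variance = [(1 − s) + s·k²](1 + CV²) − m².

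With d = (difference in means)/√[(sum of the two variances)/51], the chance of p < 0.05 is Φ(d − 1.96) + Φ(−d − 1.96).

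Worked case, 40% against 20%, k = 2, CV = 1: the variances are 2.44 and 1.76, d = 0.20/√(4.20/51) = 0.70, and the chance is 10.7%. Other results under no true difference:

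| Shares on A | k | CV | Chance of p < 0.05 |
|---|---|---|---|
| any | 1 | 1.0 | 5.0% |
| 40% v 20% | 1.5 | 1.0 | 7.1% |
| 40% v 20% | 2 | 1.0 | 10.7% |
| 40% v 20% | 3 | 1.0 | 16.7% |
| 60% v 40% | 2 | 1.0 | 9.4% |
| 75% v 25% | 2 | 1.0 | 33.8% |
| 75% v 25% | 2 | 0.75 to 1.5 | 51.6% to 18.2% |

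A moderate imbalance inflates the error rate modestly; a large inflation needs a large imbalance. On a scale where k = 1 the rate returns to 5% whatever the mix.

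**The case against.** The best case for leaving the plan alone has four parts.

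- **The premise about the unit is not in the documents.** They only expand the abbreviation. This is true. The point rests on the ordinary meaning of a defined daily dose. The plan offers no other meaning and no weighting, so the point stands as a stated assumption.
- **A consumption unit suits an endpoint called use.** Section 9.2.2 also lists medication use under economic endpoints, and for utilization DDD is defensible, which is why it should stay as a supportive analysis. As the sole scale for whether less opioid was taken, it leaves strength out.
- **Section 10 is a brief description and the SAP may add detail.** It may. But the unit is already stated, and the SAP is due only before database lock, whereas findings from the 3-month extract may be presented.
- **The data are recoverable.** Name, dose and duration are in the diary, so conversion is possible later. That makes the change cheap, but a scale chosen after results are seen is weaker evidence than one fixed beforehand.

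A reader might also infer more than the documents support. They do not show that drug mix differs between cohorts. Section 8.2 says who chooses the operation, not who prescribes the opioid or whether prescribing varies by procedure; a surgeon with one habitual prescription for both operations would produce no artefact.

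**Conclusion.** The concern holds conditionally. For objectives #8 and #10 the stated unit does not match the question, and nothing in the plan guards against a difference in drug mix. Whether bias occurs depends on two things the documents do not give: unequal strength per DDD among the opioids used, and a mix that differs between cohorts. If either is absent, the artefact is zero.

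The ratios of 1.09 to 1.29 are exact arithmetic on assumed shares and k values. It is tempting to read them as an estimate of bias in this study; they are not one.

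Two wider readings should also be resisted. The primary ASES comparison is untouched. And although objectives #9 and #11 total non-opioid prescription drugs in DDD too, no change is recommended there: morphine equivalents do not apply, counting days on drug would discard dose, and totals by drug class would still need a unit.

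**What to change.** For objectives #8 and #10 only:

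1. In Table 2, make cumulative oral morphine milligram equivalents the outcome measure.
2. Fix in the SAP, before the 3-month data extract in Section 10.6, one conversion table with its source and version, and a rule for combination products.
3. Keep the DDD total as a supportive analysis, stating the source of the DDD values.
4. Report the type of opioid by cohort, so that readers can see whether the mix differed.

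The cost is a wording change, a coding step and one descriptive table. No new data are needed. The downside is that a conversion table must be chosen and carries its own uncertainty, so any error in it leaves some drug-mix effect behind; the supportive DDD analysis helps to show how far the result depends on the scale. The change concerns measurement only and implies nothing about which drug or dose participants should receive.
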